5.1.2. Packaging and labelling

Packaging and labelling of the IMP will be performed in accordance with Good Manufacturing Practice (GMP) and national regulatory requirements.

5.2. Control treatment

The control treatment in this study is PE which is a treatment with no active substance and thus not an IMP. PE will be prepared and performed according to the standard of care at each site. 5-10 sessions of PE will be performed.

5.3. Non-Investigational Medicinal Product(s)

Non-Investigational Medicinal Products (NIMPs) will be sourced from the investigational site pharmacy supply. Essential information about the NIMPs is to be found in the latest versions of respective Summary of Product Characteristics.

The subjects will be treated with the following NIMPs (other treatments may be used as required at the investigator's discretion):

Prophylactic antibiotic (all subjects):

All subjects will receive a standard regimen of antibiotics according to local clinical practice, starting before the first treatment and continuing until IgG levels return to acceptable values, as judged by the investigator.

Premedication (imlifidase arm):

All subjects in the imlifidase arm, will be given antihistamine (orally) as pretreatment before imlifidase infusion.

Treatment schedule for steroid dosing (all subjects):

Day 1: Methylprednisolone 500 mg as premedication before treatment
Day 2-3: Methylprednisolone 500 mg daily
Day 4: Prednisolone/prednisone 60 mg
Day 5: Prednisolone/prednisone 50 mg
Day 6: Prednisolone/prednisone 40 mg
Day 7: Prednisolone/prednisone 30 mg
Day 8: Prednisolone/prednisone 20 mg will continue daily for 1 week, followed by 10 mg daily for 1 week and thereafter 5 mg daily throughout the study

Treatment with IVIg (all subjects)

Imlifidase arm: subjects will be given a high dose of IVIg (2 g/kg BW, maximum of 140 g), on day 4 (may be given over 2 days, as judged by the investigator). If a subject in this arm has to be treated with PE for medical reasons, IVIg will be given after the last session of PE.

PE arm: a high dose of IVIg (2 g/kg BW, maximum of 140 g) will be given after the last session of PE (may be given over 2 days, as judged by the investigator).

Treatment with Rituximab (all subjects)

A single dose of rituximab, 375 mg/m², will be given to all subjects 5 days after completion of the IVIg infusion.

Rituximab requires use of contraception for 12 months after treatment. Women of childbearing potential will be encouraged to continue using highly effective contraceptive method for at least 6 months after end of study.

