4.2. Inclusion Criteria

1. Signed Informed Consent obtained before any study-related procedures
2. Willingness and ability to comply with the protocol
3. Male and/or female donor kidney recipients age ≥ 18 years at the time of screening
4. Presence of DSA(s)
5. Meet the Banff 2017 criteria for active or chronic active AMR
6. At least 25% rise in serum creatinine compared to last individual value taken prior to the AMR. Patients with delayed graft function and AMR within 10 days after transplant (confirmed by kidney biopsy) can be included regardless of serum creatinine level
7. Women of child-bearing potential willing or able to use at least one highly effective contraceptive method throughout the study. In the context of this study, an effective method is defined as those which result in low failure rate (i.e. less than 1% per year) when used consistently and correctly such as:
 - combined (estrogen and progestogen containing) hormonal contraception associated with inhibition of ovulation
 - oral
 - intravaginal
 - transdermal
 - progestogen-only hormonal contraception associated with inhibition of ovulation
 - oral
 - injectable
 - implantable
 - intrauterine device (IUD)
 - intrauterine hormone-releasing system (IUS)
 - bilateral tubal occlusion
 - vasectomised partner
 - true abstinence: When this is in line with the preferred and usual lifestyle of the subject. [Periodic abstinence (such as calendar, ovulation, symptothermal, post-ovulation methods) and withdrawal are not acceptable methods of contraception]
8. Men willing to use double-barrier contraception from the first day of treatment until at least 2 months after the dose of imlifidase, if not abstinent

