6.1.2. Visit 2 (treatment), Day 1-5

The following activities and assessments will be performed on day 1, prior to start of treatment with imlifidase or PE:

- Blood pressure, pulse rate and respiratory frequency, and body temperature
- Baseline samples for DSA, PK, PD, and ADA (IgG) will be collected prior to start of treatment
- P-creatinine
- Urine sample for measurement of albumin/creatinine ratio

Imlifidase arm: Methylprednisolone, antihistamine and antibiotic prophylaxis will be administered before the imlifidase infusion.

PE arm: Methylprednisolone and antibiotic prophylaxis will be administered before the first treatment.

Treatment with antibiotics will continue until IgG levels return to acceptable values as judged by the investigator. Methylprednisolone will be administered according to treatment schedule, see [Section 5.3](#).

The following activities will be performed after the start of treatment:

- Blood pressure and pulse rate will be monitored at 2, 6, 24, 48, 72, and 96 hours
- Respiratory frequency and body temperature will be monitored at 24, 48, 72, and 96 hours
- Safety laboratory tests ([Table 5](#)) will be collected at 24, 48, 72, and 96 hours
- Urine sample for measurement of albumin/creatinine ratio at 24, 48, 72, and 96 hours.
- Imlifidase arm: Samples for PK will be collected at 30 minutes and 1 hour
- Samples for DSA, PK and PD will be collected at 2 and 6 hours
- Samples for DSA, PK, PD and ADA (IgG) will be collected 24 hours after treatment.
- Samples for DSA, PK and PD will be collected at 48, 72, and 96 hours. The 72-hour sample must be taken prior to high dose IVIg is given in the imlifidase arm

Imlifidase arm: High dose IVIg will be given on day 4 (at least 72 hours after the imlifidase infusion). Dose may be given over 2 days as judged by the investigator.

6.1.3. Visit 3, Day 6

The following activities and assessments will be performed:

- Blood pressure, pulse rate and body temperature will be monitored
- Safety laboratory tests (Table 5) will be collected
- Samples for DSA, PK and PD will be collected
- Urine sample for measurement of albumin/creatinine ratio

6.1.4. Visit 4, Day 8

The following activities and assessments will be performed:

- Blood pressure, pulse rate and body temperature will be monitored
- Safety laboratory tests (Table 5) will be collected
- Urine sample for measurement of albumin/creatinine ratio
- Samples for DSA, PK, PD and ADA (IgG) will be collected

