6.1.10. Visit 11 (follow up, end of study), day 180 (+/- 14 days)

The following activities and assessments will be performed:

- Physical examination
- Blood pressure, pulse rate and body temperature will be monitored
- Safety laboratory tests (Table 5) will be collected
- ECG
- Pregnancy test (serum)
- Urine sample for measurement of albumin/creatinine ratio
- Kidney biopsy will be performed
- Samples for DSA, PD and ADA (IgG) will be collected

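### The men's contraception period has no end point in the PE arm and does not match the 12-month rituximab statement; the women's minimum nearly meets it, depending on what end of study means

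*Protocol*

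**What the plan says.** Protocol section 5.3 gives a single dose of rituximab to every subject in both arms, 5 days after IVIg is completed. It then makes two statements about contraception:

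- "Rituximab requires use of contraception for 12 months after treatment". No sex or arm is named.
- "Women of childbearing potential will be encouraged to continue using highly effective contraceptive method for at least 6 months after end of study".

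Section 4.2 sets the eligibility rules:

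- Criterion 7: "Women of child-bearing potential willing or able to use at least one highly effective contraceptive method throughout the study".
- Criterion 8: "Men willing to use double-barrier contraception from the first day of treatment until at least 2 months after the dose of imlifidase", unless abstinent. It is not limited to one arm.

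The protocol uses the term end of study in two ways. Section 3.4 defines it as the last visit of the last subject. Section 6.1.10 attaches it to each subject's own final visit: "Visit 11 (follow up, end of study), day 180 (+/- 14 days".

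**The concern.** For men, the end of the period hangs on an event that occurs in only one arm. Sections 1.2 and 3.1 give PE-arm subjects plasma exchange and make no provision for imlifidase. An investigator therefore cannot tell a man in that arm when his period ends. In the imlifidase arm the end is defined, but it comes long before 12 months after rituximab, which those men also receive.

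For women, the 12 months run from rituximab and the 6 months run from end of study. Whether the second period satisfies the first depends on the visit date and on which meaning of end of study applies. The strength of the wording also falls. The first sentence states a requirement, the second only encourages, and criterion 7 asks for "at least one highly effective contraceptive method throughout the study" and no longer.

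What is at stake is a reproductive-safety instruction that feeds eligibility and consent. No endpoint, sample size or analysis depends on it.

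**Working it through.** The protocol states no end dates for these periods, so there is no figure to reproduce. The check is date arithmetic, with 2 months = 61 days, 6 months = 183 days and 12 months = 365 days. Using a month of 365.25/12 days changes each result by less than one day.

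**Day of rituximab**

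- Imlifidase arm: IVIg on Day 4, possibly over 2 days (sections 5.3 and 6.1.2), so it is complete on Day 4 or 5. Adding 5 days gives Day 9 to 10. This assumes no added PE; section 5.3 moves IVIg to after the last PE session if PE is needed.
- PE arm: 5 to 10 sessions, then IVIg. The protocol does not state the interval between sessions, so daily to every other day is an assumption. Five daily sessions end on Day 5, IVIg is complete on Day 5 or 6, and rituximab falls on Day 10 to 11. Ten sessions every other day end on Day 1 + 9 × 2 = 19, IVIg is complete on Day 19 or 20, and rituximab falls on Day 24 to 25.

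**Twelve months after rituximab**

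- Imlifidase arm: 9 + 365 = 374 to 10 + 365 = 375.
- PE arm: 10 + 365 = 375 to 25 + 365 = 390.

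**Men**

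- Imlifidase arm: Day 1 + 61 = Day 62. The difference from Day 374 is 312 days, about 10 months.
- PE arm: there is no imlifidase dose, so no date can be calculated.

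**Women, counting from the subject's own Visit 11**

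The minimum ends at Visit 11 + 183 days:

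| Visit 11 | Minimum ends | Imlifidase arm (374 to 375) | PE arm (375 to 390) |
|---|---|---|---|
| Day 166 | 349 | 25 to 26 days short | 26 to 41 days short |
| Day 180 | 363 | 11 to 12 days short | 12 to 27 days short |
| Day 194 | 377 | 2 to 3 days over | 2 days over to 13 days short |

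Table 3 of the SAP puts rituximab in the PE arm 3 to 4 days after IVIg, where the protocol says 5. That would bring the PE-arm dates forward by 1 to 2 days and leaves the picture unchanged.

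**Women, counting from last subject last visit**

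The Day 180 shortfall disappears for any woman whose own Visit 11 precedes the last subject's by at least that many days: 11 to 12 in the imlifidase arm, 12 to 27 in the PE arm. With recruitment extended to 35 months (section 3.2), that would be most women.

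**The case against.** The strongest reply concerns the women. A reader might infer that 12 months and 6 months contradict each other outright. They do not, because they start from different events. Women are already covered on study by criterion 7, and the 6 months are added to that. The second sentence reads as a way of carrying out the first in whole months, with a minimum rather than a fixed length. At the late edge of the visit window the imlifidase-arm shortfall is gone, and under the section 3.4 definition it rarely arises. All of this stands. What it leaves is a small, conditional shortfall and an ambiguous term.

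A reader might also infer that most subjects would fall short of the protocol's own requirement. The documents do not support that. The day counts concern women of childbearing potential only, and no sex or age mix is given. The claim extends to men only if the 12-month sentence covers them. It names no sex, but the one instruction that follows it is addressed to women. The text allows either reading and settles neither.

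Encouragement may simply reflect that a protocol can advise but hardly enforce conduct after a subject has left. That is fair, but it does not explain why the preceding sentence states a requirement. Section 5.3 also refers sites to the product information for the non-investigational products, and the consent pages are not in the text available for review. What subjects were actually told therefore cannot be judged.

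On criterion 8, one can say that it is a statement of willingness checked before randomisation and is meant to bite only if imlifidase is given. That is a plausible intention, but the criterion does not say so.

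**Conclusion.** The men's point holds without any scheduling assumption for the PE arm: criterion 8 has no end point there. In the imlifidase arm its 2 months end at about Day 62. The 12-month sentence would run to about Day 374 to 375 if it applies to men, and the protocol does not say whether it does.

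The women's point is smaller. The two sentences in section 5.3 nearly coincide. If end of study means the subject's own Visit 11, the minimum at Day 180 falls 11 to 12 days short in the imlifidase arm, and 12 to 27 days short in the PE arm under the assumed session interval. If it means last subject last visit, most women would be covered. The drop from requiring to encouraging, and the on-study limit in criterion 7, remain under either reading.

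This is a wording inconsistency in a safety instruction. It should be corrected because the instruction, followed as written, can miss the protocol's own stated requirement or has no end. It changes no statistical figure. Nothing here implies which period is the right one.

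**What to change.** Reconcile criteria 7 and 8 in section 4.2 with the rituximab paragraph in section 5.3 so that:

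- each period is counted from the event that creates the requirement;
- each period has a defined end for both sexes in both arms, or the 12-month sentence says whom it covers;
- the text says plainly whether the period after the study is required or advised;
- end of study carries one meaning wherever a period is counted from it.

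The durations are for the sponsor's clinical team to set. The cost is rewording in two protocol sections and, where it repeats them, the consent form. No data collection or analysis changes.

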5.3.1. Conditions for Storage and Use

The investigator will ensure that the NIMPs will be stored in appropriate conditions, according to labels, in a secure location with controlled access. The storage compartment shall be monitored regularly, and the temperature shall be documented.

5.4. Blinding

This is an open-label study. Due to the nature of the control treatment, blinding of the control treatment is not feasible.

5.5. Compliance, Accountability and Destruction of IMP(s) and NIMP(s)

5.5.1. Compliance

The administration of all medication (including investigational products) will be done by trained study personnel and must be recorded in the appropriate sections of the eCRF. All investigational treatments must also be documented in the accountability logs. Treatment compliance will be assured by supervised administration of the investigational product by the investigator or delegate. The dose, date and time of administration of the investigational product will be checked by the monitor at monitoring visits.

5.5.2. Accountability and Destruction of IMP(s) and NIMP(s)

It is the principal investigator's/institution's responsibility to establish a system for handling study treatments, including investigational medicinal products, to ensure that:

1. Deliveries are correctly received by a responsible person (e.g. pharmacist or designated study personnel)
2. Deliveries are recorded
3. All IMP and NIMPs are handled and stored safely and properly
4. The IMP provided for this study will be used only as directed in the study protocol
5. The study personnel will account for all drugs dispensed and returned. Any discrepancies must be documented, investigated and appropriately resolved
6. The study pharmacist will maintain and keep the total accountability records. At the end of the study, the pharmacist will return all unused IMPs to Hansa Biopharma for destruction after it has been checked by monitor. The used IMP vials will be accounted for and destructed at site, after control by monitor.

5.6. Product Quality Complaints

A PQC is a reported defect related to the identity, quality, durability, reliability, safety, effectiveness, or performance of a product after it is released for distribution and/or usage. The defect can be related to the product itself or to the product's label, delivery system, or packaging. Examples of PQCs include but are not limited to contamination, label errors, and delivery system failures.

Hansa Biopharma must be made aware of any PQCs as soon as possible on the day of detection. Hansa Biopharma will assess the impact of the reported defect and take any necessary precautions to ensure the safety of the study subjects and the credibility of the study results. PQCs should be reported using the IMP Issue form to ensure that all relevant information is captured.

5.7. Concomitant Medication(s) and Therapy

Maintenance immunosuppression such as tacrolimus, mycophenolate mofetil, cyclosporine A, prednisolone and others are prescribed at the discretion of the treating physician or investigator according to SOC. These drugs can be used the same day as the infusion of imlifidase and be continued during the treatment of AMR. No specific maintenance immunosuppressive treatment in addition to what the patient already has is needed within the study.

Other concomitant medication and/or other therapy considered necessary for the patient's welfare may be given at the discretion of the investigator. All concomitant medication and other therapy, including i.e., premedication, prophylactic antibiotics, steroids and PE, must be recorded on the concomitant medication page in the CRF throughout the study, beginning from screening to end of study. Recorded information will include indication, name of drug or therapy, dose (if available), route of administration and start and stop date.

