Imlifidase is an IgG-degrading enzyme of *Streptococcus pyogenes* that cleaves all four human subclasses of IgG with strict specificity. Imlifidase hydrolyzes human IgG below the hinge region thereby generating one F(ab')₂ fragment and one Fc-fragment which does not bind to Fcγ-receptors and does not activate complement. Thus, the proteolytic activity of imlifidase on IgG molecules prevents IgG mediated phagocytosis, antibody-dependent cellular cytotoxicity and complement mediated injury (Winstedt et al. 2015; Jarnum et al. 2017). Imlifidase is highly specific towards IgG and other Ig molecules, i.e. IgA, IgD, IgE and IgM, are not cleaved and no other substrates have been identified. Apart from imlifidase restricted target specificity, the speed of the reaction is a major advantage of imlifidase. Within a few hours after dosing, the

entire pool of IgG is fully cleaved into F(ab')₂ and Fc fragments thereby creating a window where IgG levels are kept very low for approximately one week.

Repeat dose toxicology studies have been performed in rabbit and dog and the no observed adverse effect level (NOAEL) was set to 2 mg/kg and lowest observed adverse effect level (LOAEL) to 20 mg/kg in both species.

Previous clinical experience with imlifidase

Six studies with imlifidase have been completed:

1. First human study, to assess the safety and tolerability of the IgG cleaving enzyme from the *Streptococcus pyogenes* Immunoglobulin G degrading enzyme of (11-HMedIdeS-01, EudraCT no. 2012-000 969-21).
2. A study to evaluate the safety and efficacy of imlifidase in Chronic Kidney Disease Patients (CKD) (13-HMedIdeS-02, EudraCT no. 2013-005417-13)
3. A phase II study to evaluate the safety, tolerability, efficacy and pharmacokinetics of intravenous ascending doses of imlifidase in kidney transplantation in sensitized patients (13-HMedIdeS-03, EudraCT no. 2014-000712-34)
4. A phase II pilot study to evaluate the safety, tolerability, efficacy, pharmacodynamics and pharmacokinetics of imlifidase in asymptomatic antibody-mediated thrombotic thrombocytopenic purpura (TTP), in patients with low ADAMTS13 (15-HMedIdeS-08, EudraCT no. 2016-000249-30).
5. A phase I/II study to assess safety, tolerability and efficacy of imlifidase given immediately prior to kidney transplantation to reduce DSAs in highly sensitized CKD patients awaiting DD kidney transplantation (14-HMedIdeS-04, FDA IND 124301)

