As for all biologics, there is a risk of infusion reactions associated with imlifidase treatment. Three non-serious and one serious infusion related reactions regarded as related to treatment have occurred in 114 subjects receiving imlifidase. Signs and symptoms associated with infusion related reactions included, but were not limited to dyspnoea, pharyngeal oedema, sinus tachycardia, chest discomfort and flushing. To mitigate the risk of infusion related reactions, all subjects receive glucocorticoid and antihistamine treatment prior to dosing and are closely monitored during the infusions.

In vitro studies have revealed that imlifidase cleaves biologics originating from rabbit and human IgG including; thymoglobulin, IVIg, basiliximab, alemtuzumab, rituximab, adalimumab, denosumab, belatacept and etanercept. The optimal interval between imlifidase administration and these biologics has not been tested (2018-003R).

The rationale for the 3-day window between imlifidase and IVIg dosing is aimed to prevent cleavage of the IVIg based on the pharmacokinetic and pharmacodynamic profiles of imlifidase. In one of the clinical studies (14-HMedIdeS-04), alemtuzumab was given four days post dosing of imlifidase and in one clinical study (15-HMedIdeS-06), IVIg was given seven days post dosing of imlifidase.

Adverse events after administration of IVIg do occur but are seldom serious. There is a very small risk of anaphylaxis, often in subjects with severe IgA deficiency. Other reported side effects include headache, myalgia, transient hypotension and flushing (all of which can be corrected by slowing the infusion rate), meningism, aseptic meningitis, skin reactions (especially eczema), neutropenia, worsening of renal failure, and thromboembolic events (DVT, MI and stroke) attributable to hyperviscosity ([Hughes et al. 2014](#)).

As an extra safety measure for women of child bearing potential, the requirement for highly effective contraception is part of the inclusion criteria for this study. Additionally, a pregnancy test will be performed at the screening visit to ensure the patient is not pregnant.

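### Section 5.7 permits maintenance immunosuppression on the day of imlifidase without excepting the biologics that section 1.3 says the enzyme cleaves in vitro

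*Protocol*

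**What the plan says.** Protocol section 5.7 opens with a list that is illustrative, not closed: "Maintenance immunosuppression such as tacrolimus, mycophenolate mofetil, cyclosporine A, prednisolone and others are prescribed at the discretion of the treating physician". The next sentence grants a general permission: "These drugs can be used the same day as the infusion of imlifidase and be continued during the treatment of AMR". The section then leaves any other medication to the investigator's discretion and requires all of it to be recorded. It does not refer to section 1.3 and gives no spacing rule.

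Protocol section 1.3 describes the interaction: "In vitro studies have revealed that imlifidase cleaves biologics originating from rabbit and human IgG including; thymoglobulin, IVIg, basiliximab, alemtuzumab, rituximab, adalimumab, denosumab, belatacept"; the list ends with etanercept. It continues: "The optimal interval between imlifidase administration and these biologics has not been tested (2018-003R". For one of these products the protocol acts. Section 1.3 explains: "The rationale for the 3-day window between imlifidase and IVIg dosing is aimed to prevent cleavage of the IVIg". Section 6.1.2 puts this into the schedule: "High dose IVIg will be given on day 4 (at least 72 hours after the imlifidase infusion".

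**The concern.** Section 1.3 is background on benefit and risk. Section 5.7 is what a site consults when deciding whether to give today's maintenance drug, and its answer for the infusion day is an unqualified yes. That suits the drugs it names. It does not suit a maintenance drug that is itself a substrate of the enzyme, and belatacept, named in section 1.3, could be such a drug.

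At stake is a dose of immunosuppression. A site that follows section 5.7 as written could give belatacept on the infusion day to a patient in active rejection, and part or all of that dose might be cleaved. The protocol guards against this for IVIg, so its instructions for two products on the same list pull in different directions.

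**Working it through.** No sample size, power or event figure is involved. The check compares the text of the relevant sections.

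**1. Do the two lists overlap?**

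- Named in 5.7: tacrolimus, mycophenolate mofetil, cyclosporine A, prednisolone. That is 4 drugs.
- Named in 1.3 as cleaved in vitro: thymoglobulin, IVIg, basiliximab, alemtuzumab, rituximab, adalimumab, denosumab, belatacept, etanercept. That is 9 products.
- On both lists: 0.

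The same-day sentence is therefore unobjectionable for the four named drugs. The gap lies in the open ending of the list.

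**2. Can the open ending reach a listed product?** Taken literally, it covers any maintenance immunosuppressant a physician prescribes. Section 5.7 also says nothing need be added to the patient's existing maintenance regimen, so continuing that regimen is the default. Belatacept is reached if a patient is already on it as maintenance. The documents never say that it is used this way; it appears only in the 1.3 list. This step is an assumption.

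**3. Is the enzyme active on the infusion day?** Section 1.1 says that within a few hours of dosing the "entire pool of IgG is fully cleaved into" fragments. That supports activity on the same day. The same section describes imlifidase as "creating a window where IgG levels are kept very low for approximately one week", but this describes IgG levels and does not show how long cleaving activity lasts, so nothing here rests on it.

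**4. How does the protocol space the listed products it does schedule?**

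- IVIg: 3 days × 24 h = 72 h, and Day 1 + 3 days = Day 4. Sections 1.3, 5.3 and 6.1.2 agree.
- Rituximab: 5 days after IVIg is completed (section 5.3), so later still.
- Earlier studies cited in 1.3: alemtuzumab four days and IVIg seven days after imlifidase.

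Every interval given for a listed product dosed after imlifidase is at least 3 days. Only the general permission in 5.7 allows none.

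**5. Does anything else close the gap?**

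- Section 4.3: no exclusion criterion names belatacept or cleaved biologics as a class.
- Section 5.3: sets timing for the study IVIg and rituximab only.
- Section 5.7, second paragraph: discretion and recording, with no spacing.
- SAP section 3.2: gives use of prohibited or discouraged medication as an example of a major deviation, but the protocol supplied lists no such drugs.

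The protocol supplied is the US version. SAP section 1 says the country versions differ slightly in some exclusion criteria, so this check covers the US text only.

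**The case against.** The strongest reply is that the key link comes from outside the documents. Nothing in them classes belatacept as maintenance therapy or says that anyone in this trial takes it. The natural reading of an illustrative list is more of the same kind, and none of the four examples is a biologic. The sentence is permissive and obliges no one to give a cleaved drug. Section 1.3 already warns by name, refers investigators to the Investigator's Brochure (not supplied, and possibly giving an interval) and describes the sites as experienced with biological drugs. Exclusion criteria 7 and 10 also let the investigator keep out a patient judged at risk or unsuitable.

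Most of this stands as a limit on size. The belatacept assumption must be stated openly, and if the brochure gives an interval, what is missing is only a cross-reference. But disclosure in a background section does not correct an unqualified permission in the operative one, and recording a dose does not prevent it.

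Two stronger readings are tempting, and neither is supported. A reader might count how many hours a same-day dose falls short of 72, or set 72 hours against the half-life of imlifidase. The 72-hour window is stated for IVIg, and section 1.3 says no best interval has been tested for these biologics, so there is no belatacept standard to fall short of. A reader might also infer harm to patients or distortion of the comparison between arms. The cleavage evidence is in vitro. Every patient also receives methylprednisolone 500 mg on days 1 to 3, a steroid taper, IVIg and rituximab, and nothing in the documents links a cleaved maintenance dose to the primary DSA endpoint.

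**Conclusion.** The point holds as a minor, inexpensive improvement to the wording. Section 5.7 states a permission wider than the protocol's own account of the drug justifies, and it conflicts with the precaution taken for IVIg.

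The practical consequence depends on one assumption, that some enrolled kidney recipients are on belatacept maintenance. The number is unknown and could be anywhere from 0 to the 20 subjects planned for imlifidase. The clinical effect of losing part of a dose is also unknown. No bias, no effect on the primary endpoint and no undisclosed risk is claimed. The benefit of the change is plausible but cannot be quantified from the documents.

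**What to change.** In section 5.7:

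- Limit the same-day permission to drugs that imlifidase does not cleave, such as the four already named, and refer to the list in section 1.3.
- Add a sentence along these lines: *A biologic listed in section 1.3, such as belatacept, should not be given on the day of imlifidase, nor until the interval supported by the Investigator's Brochure or the sponsor's PK/PD data has passed, unless the investigator judges waiting to be unsafe. If no such interval exists, wait at least the 72 hours used for IVIg.*

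The 72 hours is a fallback borrowed from the IVIg rule, not an interval shown to be safe for belatacept.

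The cost is one or two sentences and an occasional deferred maintenance dose in a patient being treated for rejection, which is why the override is needed. The change does nothing for belatacept given earlier and still circulating at the time of infusion.
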